10.0. Baseline Characteristics

10.1. Demographics

Summary statistics will be presented for age (years), gender (male or female), race and ethnicity, presentation center, pertinent medical history including illicit drug use, primary diagnosis (ICH vs. ICH with IVH), hypertension history, diabetes, anticoagulation, tobacco and cocaine use, and antiplatelet drug use.

10.2. Medical History

Summary statistics will also be presented for medical history, as well as presentation variables: temperature, pulse, systolic blood pressure, diastolic blood pressure, presenting NIHSS, GCS, ICP, ICH volume, IVH volume, extent of white matter disease (van Sweiten index), and location of bleed.

11.0. Efficacy Analyses

11.1. Primary Efficacy Analysis: Dichotomized, Adjudicated mRS 0-3 vs. 4-6 at 365 Days Post Ictus

This primary analysis will produce an estimate and 95% confidence interval for the average treatment effect comparing assignment to MIS+rt-PA treatment (MISTIE) versus control (standard of care, i.e., medical management), using the ITT principle. Specifically, we will estimate the difference between the probability of an adjudicated mRS score of 3 or less at 365 days post-stroke comparing assignment to

treatment versus control; this difference is called the average treatment effect. Below is a description of the procedure for computing estimators of the average treatment effect. We also will test the null hypothesis of zero treatment effect at level 0.05.

To estimate the average treatment effect, we will use the targeted maximum likelihood estimator (TMLE) of van der Laan and Gruber.³ This estimator adjusts for baseline (i.e., pre-randomization) variables in order to improve precision. The baseline variables, denoted by the vector B, include the three variables used in the covariate-adaptive randomization as given in Section 6.0 (i.e., pre-randomization clot volume, age, and baseline severity of impairment as measured by GCS) as well as the following additional variables: IVH volume and location of ICH (indicator of lobar vs. deep). All baseline variables are treated as categorical and included as main terms in the models below.

The TMLE estimator also involves adjustment with the goal of reducing bias due to informative censoring, that is, participant dropout that may be correlated with the primary outcome. The TMLE adjusts for missing outcomes through a combination of inverse probability of censoring weights and outcome prediction models. Specifically, the weights and prediction models use the aforementioned baseline variables, study arm, and the following post-randomization variables: mRS scores measured at 30, 180, 365 days from ictus, denoted M₃₀, M₁₈₀, M₃₆₅ respectively. The motivation is that if mRS score at a given visit is correlated with the mRS score at the next visit and also with dropout, then adjusting for observed differences in the mRS history of those who drop out versus those who stay on study may reduce bias (under the assumption that censoring is missing at random). As we describe below, this adjustment is implemented by fitting models for dropout and models for the primary outcome based on mRS measured at the previous visit, study arm, and baseline variables.

Let A denote the study arm, where A=1 for the MISTIE treatment arm and A=0 for the standard of care (medical management) arm. Let C_{30} , C_{180} , C_{365} denote the indicator of being uncensored at the 30-, 180-, 365-day visits, respectively. E.g., C_{180} =1 means the participant attended the 180-day visit and had his or her mRS M_{180} recorded.

The TMLE involves first constructing inverse probability of censoring weights W₃₀, W₁₈₀, W₃₆₅, defined as follows:

$$\begin{split} & W_{30} = 1/[\Pr(C_{30} = 1 \mid B, A) \; P(A \mid B)] \\ & W_{180} = W_{30}/\Pr(C_{180} = 1 \mid C_{30} = 1, B, A, M_{30}) \\ & W_{365} = W_{180}/\Pr(C_{365} = 1 \mid C_{180} = 1, B, A, M_{180}) \end{split}$$

where the probabilities are estimated by fitting logistic regression models. Specifically, we fit logistic regression models for the probability of censoring at each visit given mRS at the previous visit, study arm, and baseline variables, among those who attended the previous visit. Each model includes main terms and an intercept, e.g., the model

 $Pr(C_{365}=1 | C_{180}=1, B, A, M_{180}) = logit^{-1}(\beta_0 + \beta_1 B + \beta_2 A + \beta_3 M_{180})$

for the probability of remaining uncensored at 365 days given 180-day mRS, study arm, and baseline variables, is fit among those uncensored at 180 days (C_{180} =1).

We also fit a logistic regression model for the probability of A=1 given baseline variables B, used in W_{30} . When the mRS score at an interim visit (30, 180 days) is included as a covariate in a regression model, it is coded as a categorical variable. We also truncate each weight at 20 (i.e., for weights above 20 we replace them by 20). Below, there is no connection between the coefficients in different models—we

use β to denote generic coefficients in each model, for simplicity.

The TMLE involves a sequence of weighted regression model fits using the inverse probability of censoring weights constructed above. First, the weighted logistic regression model: $Pr(M_{365} \le 3 | C_{365}=1, B, A, M_{180}) = logit^{-1}(\beta_0 + \beta_1 B + \beta_2 A + \beta_3 M_{180})$ (1) using weights W_{365} is fit using all participants who are uncensored at 365 days ($C_{365}=1$). Next, for each participant who is uncensored at 180 days (the previous visit), this model fit is used to generate the predicted probability, denoted by S_{180} , of Y=1 given their 180-day mRS M_{180} , study arm A, and baseline variables B.

The above two-step process (model fitting then generating predictions) is iterated by replacing $(M_{365} \le 3)$ by S_{180} in (1) and regressing on previous visit mRS, study arm, and baseline variables.

Specifically, fit $E(S_{180} | C_{180}=1, B, A, M_{30}) = logit^{-1}(\beta_0 + \beta_1 B + \beta_2 A + \beta_3 M_{30})$ with weights W_{180} (2) using all participants who are uncensored at 180 days ($C_{180}=1$). and use the model fit to generate the predicted mean S_{30} of S_{180} for each participant with $C_{30}=1$; next, fit $E(S_{30} | C_{30}=1, B, A) = logit^{-1}(\beta_0 + \beta_1 B + \beta_2 A)$ (3) with weights W_{30} using all participants who are uncensored at 30 days ($C_{30}=1$).

Lastly, the probability of Y=1 under assignment to study arm A=1 (MISTIE treatment) is estimated by generating for every participant (in both arms) a prediction by substituting their vector of baseline variables B and setting A=1 in the model fit (3). Similarly, the probability of Y=1 under assignment to study arm A=0 (medical management) is estimated by generating for each participant (in both arms) a prediction by substituting their vector of baseline variables B and setting A=0 in the model fit (3). The primary analysis estimator of the average treatment effect as a risk difference is defined as the difference between the former and the latter.

The 95% confidence interval will be computed by the non-parametric bootstrap (resampling participants with replacement and recomputing the above estimator), and using the bias corrected and accelerated (BCa) method.⁵ The null hypothesis of zero average treatment effect will be rejected if this confidence interval excludes 0. This completes the description of the primary efficacy analysis, except for how missing baseline variables and intermittent (non-monotone) missingness are handled, as described next.

Missing baseline variables are imputed using the median for continuous-valued variables and mode for categorical variables. This and the following paragraph are done before any of the steps above.

We next describe how intermittent (non-monotone) missing data are handled, such as when a participant misses the 30-day visit only. We consider each interim visit at v=30 and 180, in turn. First, for visit v=30 days, we fit a multinomial logistic regression for M_{30} given A, B among those with C_{30} =1; for those with C_{30} =0, we then set their M_{30} to be the value with highest predicted probability from the model fit. Next, for visit v=180 days, we fit a multinomial logistic regression for M_{180} given A, B, C_{30} , among those with C_{180} =1; for those with C_{180} =0, we set their M_{180} to be the value with highest predicted probability from the model fit. Next, for visit v=180 days, we fit a multinomial logistic regression for M_{180} given A, B, C_{30} , among those with C_{180} =1; for those with C_{180} =0, we set their M_{180} to be the value with highest predicted probability from the model fit. We do not apply this process to the final outcome at 365 days. All models include intercepts and main terms for the variables listed. Next, we modify model (1) to include the additional main term $C_{30}C_{180}$ and its interaction with A. Similarly, in model (2) we include the additional main term C_{30} and its interaction with A. The idea is that each model (1)-(2) now contains an indicator of whether the mRS score on the right side was directly measured or was predicted by the above process based on previous mRS measurements, study arm, and baseline variables.

Minimally Invasive Surgery Plus rt-PA for ICH Evacuation Phase 3

We will conduct sensitivity analyses to evaluate the impact (beyond what is explained by variables used in the analysis above) of informative censoring on our estimators, following recommendations from the U.S. National Research Council Panel on Handling Missing Data in Clinical Trials.⁶

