**Multivariate Model of Outcome:** When well-established severity factors (ICH size, IVH size, presenting GCS, NIHSS) are considered, a multivariate model of outcome (mRS. 0-3 vs. 4-6), removal of clot is the third important factor in association with good outcome. Removal of clot has an OR of 0.27; (CI 0.066 to 1.07,  $p < 0.062$ ), consistent with animal models as well as the primary hypothesis that removal of clot is beneficial. The factors that produce variability have now been adequately identified and this phase III trial is appropriately powered to definitively test for the benefits of MIS+rt-PA and for the surgical importance of the clot volume reduction hypothesis.

**Figure 6.** Relationship between percent clot size reduction with MIS+rt-PA vs. end of treatment clot volume demonstrates how change in clot size increases the likelihood of good outcomes. Medical subjects show minimal clot size reduction. A range of larger and smaller reductions is demonstrated for MIS+rt-PA subjects. Large percentage of clot reduction > 60% and end of treatment clot size < 15 mL (I) was associated with increased likelihood of mRS 0-3 (OR: 3.04).

**Patient Utility:** Besides mRS, the Barthel Index and Stroke Impact Scale (SIS) provide additional insights to post-stroke recovery. These include physical recovery, such as strength, hand function, ADL, mobility, emotion, communication, memory, thinking and social participation (all on a scale of 0 to 100 with a higher score indicating better recovery). MIS+rt-PA appears to improve physical ability compared to the standard treatment at 180 days. This is supported by SIS strength (mean difference = 11.8, SD = 7.6,  $p$ -value = 0.122) and mobility (mean difference = 10.3, SD = 8.8,  $p$ -value = 0.244) scales as well as by higher proportion of patients with independence in toilet use, sphincter control and mobility on Barthel scale in MIS+rt-PA group. Importantly, the observed mean differences are within the range of change regarded as clinically important. Further, the memory score is also markedly higher in the MIS+rt-PA arm by 180 days post stroke

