3. Imaging to rule out underlying pathology. A CTA will be done prior to randomization, preferably at the time of the stability CT scan, to rule out underlying cerebro-vascular or brain pathology. If a CTA is contraindicated due to renal impairment, an MRA will be done at this time instead. In addition, an MRI will be done at baseline and repeated on day 7-10 ( $\pm 1$  day) to assess edema and cerebral ischemia and contain the following sequences: T1, MPRAGE, DWI, AXIAL FLAIR, AXIAL SWI, PWI, Axial T1 POST, and DTI. In cases where SWI of sufficient quality cannot be adequately obtained, T2W GRE may be substituted. B0 and ADC Maps should be uploaded along with the DWI B-100 images. Obtaining the baseline MRI prior to first dose of rt-PA is preferred, or obtain any time on days 1-3 per scanner availability. The requirement to obtain either MRI is waived for study centers located in Spain.

CT angiogram or routine angiogram with evaluation for “spot sign” is encouraged and considered standard of care to complete the evaluation for aneurysm, AVM, or other malformations if the CTA or MRA are inconclusive.

4. Blood pressure. Blood pressure stability is defined as SBP < 180 mmHg sustained over six hours prior to randomization.

5. NIHSS. A NIHSS score must be obtained and must be  $\geq 6$  (or a GCS of  $\leq 14$ ) for the patient to be eligible (using distal motor function). The NIHSS must be done by a certified examiner. The NIHSS must be done at the time of enrollment to confirm eligibility.

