## 9 STATISTICAL CONSIDERATIONS

### 9.1. **Statistical Analysis Plan**

**Primary Efficacy.** The primary objective of this multicenter, randomized, controlled, Phase III clinical trial is to determine the efficacy of intra-clot catheter placement and aspiration of hematoma contents, followed by gentle clot irrigation with low dose recombinant tissue plasminogen activator (rt-PA), referred to as Minimally-Invasive Surgery plus rt-PA (MIS+rt-PA). The primary hypothesis of this trial is that the MIS+rt-PA approach to intracerebral hemorrhage (ICH) management will result in more patients having overall better functional outcome at 180 days, as defined by the modified Rankin Scale (mRS) in the range 0-3, when compared to patients managed with standard aggressive medical treatment. Although the mRS includes a category for death, and hence the primary analysis incorporates mortality outcomes, mortality as a separate outcome will also be examined. An intent-to-treat (ITT) paradigm for the analyses will be incorporated. The proposed trial would enroll a total of 500 patients, 250 randomized to each treatment arm (MIS+rt-PA and medical management). The power to detect the effect size of 13% across all clot locations with this sample size is 88%. The power to detect the conservatively estimated effect size of 11% in this patient population is 81%.

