The above stopping boundaries are used after 250, 375 and 500 patients, respectively, have 180-day post-stroke measurements. If the test statistic described above exceeds the efficacy boundary, or if it is less than the futility boundary, the enrollment of patients is stopped early. The futility boundary at each interim analysis corresponds to a one-sided test at level 0.0001 of the hypothesis that the probability of a “good” outcome (mRS 0-3) is  $\geq 11\%$  under assignment to MIS+rt-PA vs medical management. These boundaries are more aggressive than the efficacy boundaries (the latter of which are based on O'Brien-Fleming boundaries, but are proportionally increased to strongly control the study-wide Type I error rate at the 5% level).

The above design has the following properties as described in Figure 1 and Table 2:

- i) At least 88% power to detect a treatment benefit  $\geq 13\%$ , assuming the probability of mRS 0-3 under medical management is 25%;

- ii) At least 81% power to detect a treatment benefit  $\geq 11\%$ , assuming the probability of mRS 0-3 under medical management is 20%.

**Table 2. Estimated Power for Risk-Difference Effect Sizesa from 10-13% (N=500) by Probability of mRS 0-3 in Medical Management Arm**

	Base Plan b	Plan B b
Effect Size	Probability = 0.25	Probability = 0.20
13%	88%	91%
12%	83%	87%
11%	76%	81%
10%	68%	73%

a MIS+rt-PA – medical management

b Tables 4, 5 in CCC grant

[figure not shown]

Figure 1. Power curves at ranges of effect sizes on risk difference scale, assuming baseline probability of modified Rankin Score 0-3 for medically-managed patients = 25%

**9.1.10. Statistical Power for Secondary Aim 2a.** Based on MISTIE II data (Table 1), the relationship between mRS score and EOT clot size is estimated as an OR (95% CI) of 3.82 (0.97-15.1,  $p=0.056$ ). Simulations were performed on 1000 generated samples of 250 patients per group based on randomized MISTIE II patient data. These simulations indicate that with 500 total patients the estimated power to detect an adjusted OR of 3.82 is  $\geq 98\%$ . Additional simulations suggest that there is  $\geq 90\%$  power for detecting an adjusted OR as low as 2.38 to evaluate the strength of the relationship between clot size, dichotomized as  $\leq 15$  vs  $> 15$  mL and mRS outcome (0-3 vs 4-6).

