8.0. Multiplicity

The primary analysis of efficacy is tested at the two-sided alpha level of 0.05. In addition, secondary analyses will consider the alpha=0.05 two-sided type I error. Secondary analyses will be examined in the order specified and will not be corrected for multiplicity of testing.

Secondaries 2-7 are defined. The other analyses without specific hypotheses are considered exploratory. We will present descriptive statistics and CIs.

For safety outcomes, we do not account for multiplicity as this study was not powered to observe safety. Thus, a cautionary approach is justified.

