11.2.3. Additional Efficacy Analysis: Severity Subgroup Analysis

Regression of the treatment by subject severity. In subsequent analyses, the model in equation (1) will be modified to include multiple baseline severity variables, such as NIHSS, IVH, extent of white matter disease, co-morbidity, etc. The models will be compared using Akaike Information Criterion (AIC) to assess the best combination of predictors. The discriminatory ability of the models will be compared using the cross-validated area under the Receiver Operating Characteristic (ROC) curve.

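### The primary model leaves out baseline NIHSS, which must be recorded at enrollment: a cheap gain in precision goes unused, of uncertain and probably small size

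*SAP*

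**What the plan says.** SAP 11.1 estimates the difference in the probability of mRS 0-3 at 365 days by TMLE. The baseline vector B holds the three covariate-adaptive randomization variables (clot volume, age, GCS), "as well as the following additional variables: IVH volume and location of ICH (indicator of lobar vs. deep"). The same paragraph says that the adjustment is there for precision and that every baseline variable enters in categories.

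On NIHSS, the documents say:

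- Protocol 2.2, in the paragraph on the multivariate model of outcome, lists four factors together: "When well-established severity factors (ICH size, IVH size, presenting GCS, NIHSS) are considered". The primary model uses the other three.
- Protocol 4.3.1, item 5, calls for a certified examiner and adds: "The NIHSS must be done at the time of enrollment to confirm eligibility".
- SAP 11.2.3 brings NIHSS in only afterwards: "the model in equation (1) will be modified to include multiple baseline severity variables, such as NIHSS, IVH, extent of white matter disease". Those models are compared by AIC and cross-validated ROC area. Protocol 9.1.7.a has a similar sentence.
- SAP 5.5, in its subgroup plan, names NIHSS in brackets as an alternative to GCS.

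Neither document explains why NIHSS is absent from the primary list.

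**The concern.** The variable appears to meet every test for a primary covariate. It is measured before allocation, it should be nearly complete because eligibility depends on it, and the protocol itself treats it as prognostic. If it predicts outcome beyond the five planned covariates, including it narrows the primary confidence interval with no new data.

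Two features of the plan suggest that GCS may not carry all of this information. The only GCS cut points given (SAP 5.5) are 3-8, 9-12 and 13-15, so a categorical GCS is coarse. And Protocol 4.1.1 admits patients with GCS of 14 or less or NIHSS of 6 or more, so a patient with GCS 15 can enter only through NIHSS.

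What is at stake is some width of the primary interval. The validity of the primary test is not in question.

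**Working it through.** **1. Reproduce the stated power.** Inputs: "The primary analysis of efficacy is tested at the two-sided alpha level of 0.05" (SAP 8.0); "The proposed trial would enroll a total of 500 patients, 250 randomized to each treatment arm" (Protocol 9.1); "The power to detect the effect size of 13% across all clot locations with this sample size is 88" percent (Protocol 9.1); "assuming the probability of mRS 0-3 under medical management is 25" percent (Protocol 9.1.9). The rates are therefore 25% and 38%.

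- Null SE, with pooled rate 0.315: √(2 × 0.315 × 0.685 / 250) = 0.04155.
- Alternative SE: √((0.25 × 0.75 + 0.38 × 0.62) / 250) = 0.04114.
- Power: Φ((0.13 − 1.96 × 0.04155) / 0.04114) = Φ(1.18) = 88.1%.

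With the three-look boundaries of Protocol Table 1 power is 87.7%. With the SAP 12.0 two-look design it is 87.9%. The stated 88% thus comes from unadjusted proportions and depends on no covariate.

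**2. Simulate the effect of adding NIHSS.** Neither document gives the NIHSS-GCS correlation or the NIHSS effect given the other covariates, so both were varied as assumptions. Set-up:

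- 2,000 trials per scenario, N = 500, 25% vs 38%, simple 1:1 allocation, complete data, logistic standardization to a risk difference.
- Assumed log odds ratios for a good outcome per SD: age −0.8, GCS 1.0, ICH volume −0.3, IVH volume −0.3; lobar location 0.3, with 38% lobar.
- The five planned covariates were coded in categories. NIHSS was then added either as three categories or as one linear term.

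The table shows the change in variance of the risk difference against the five-covariate model, and the power Φ(0.13/SE − 1.96) without and with the linear term.

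| Size of NIHSS-GCS correlation | NIHSS OR per SD, given the rest | 3 categories | Linear | Power, linear term |
|---|---|---|---|---|
| 0.50 | 1.00 | +0.2% | −0.1% | 94.9 → 94.9% |
| 0.50 | 0.74 | +0.2% | −1.2% | 93.4 → 93.7% |
| 0.50 | 0.55 | −3.7% | −5.5% | 94.2 → 95.2% |
| 0.50 | 0.41 | −6.5% | −9.5% | 95.2 → 96.8% |
| 0.70 | 1.00 | +0.3% | −0.2% | 93.3 → 93.3% |
| 0.70 | 0.74 | −1.0% | −2.6% | 93.6 → 94.2% |
| 0.70 | 0.55 | −4.4% | −7.5% | 94.5 → 95.9% |
| 0.70 | 0.41 | −5.3% | −9.6% | 95.3 → 96.9% |
| 0.85 | 1.00 | +0.8% | −0.6% | 93.3 → 93.4% |
| 0.85 | 0.74 | −1.2% | −1.7% | 94.4 → 94.7% |
| 0.85 | 0.55 | −3.6% | −8.6% | 94.3 → 95.9% |
| 0.85 | 0.41 | −5.3% | −9.5% | 96.2 → 97.6% |

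The five planned covariates alone cut variance by about 16% to 24% against no adjustment. A linear NIHSS term then costs essentially nothing when it has no effect of its own, and gains up to about 10% at the strongest effect tried. The gain in power is 0 to 1.6 points. In three categories the change in power is −0.2 to +1.1 points.

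A separate N = 500 simulation over the milder range, OR 0.8 to 0.5 per SD, put the linear term's gain at about 1% to 6% of variance, and at essentially nothing when NIHSS has no effect beyond GCS.

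**3. Translate into patients.** A variance cut of r is worth 500/(1 − r) − 500 patients: about 5 at 1%, 32 at 6% and 56 at 10%.

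**4. A caution on scale.** Applied to the unadjusted (unpooled) figure of 88.5%, a 5% cut gives 90.0% and a 10% cut gives 91.5%. Those steps exceed the gains in the table because the adjusted analysis already starts from higher power. The adjusted analysis is the right comparison.

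The table's simulation does not reproduce the censoring weights, the covariate-adaptive allocation or the bootstrap interval.

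**The case against.** The case for leaving the plan alone has real weight.

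- **No rule is broken.** The covariates are prespecified on a stated basis: the randomization variables plus two established severity variables (SAP 2.2). This stands. The proposal is for a sixth covariate.
- **GCS already measures severity.** SAP 5.5 treats the two scales as alternatives, and the phase II outcome table in Protocol 2.2 has a GCS term but no NIHSS term. This stands as a reason for doubt about the gain. It does not show that the gain is nil, and the SAP 5.5 wording concerns exploratory subgroups.
- **Adding NIHSS is not free.** Under the categorical rule it would need cut points and several coefficients, and it raised variance by up to 0.8% when it had no effect of its own. This applies to the three-category form. A linear term avoids it but needs an exception to the rule. The censoring models are sparse: at the 2% loss cited in SAP 9.0, 2% × 500 = 10 dropouts are spread over three visits. That objection also stands, for those models.
- **NIHSS-adjusted analyses are already planned.** They are, and they are labelled non-primary. One could argue that a prespecified primary NIHSS term removes any temptation to prefer a later adjusted result. That argument is weak: the hierarchy already fixes one primary analysis, and models with comorbidity and white matter disease would remain.

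A reader might infer that precision is certainly being lost, or that the change has no downside. The documents support neither, because they report no NIHSS effect beyond GCS and the extra terms carry a small cost.

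**Conclusion.** The point holds as a suggestion for improvement. The plan omits a baseline variable that it collects for every eligible patient and itself describes as prognostic, from an analysis whose adjustment is meant to buy precision, and it gives no reason.

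The likely benefit is small: about 0 to 6% lower variance, up to about 10% at the strongest effects tried, or roughly 0 to 1.6 points of power. This rests on assumed NIHSS effects and correlations and on complete-data simulation.

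It would be wrong to read the omission as a source of bias or type I error, or as undermining the stated power. Randomization protects the first two, and the 88% reproduces with no covariates at all.

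**What to change.** Before unblinding, amend SAP 11.1 as follows:

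- Add baseline NIHSS as one linear term in outcome models (1), (2) and (3). Specify that this is the value obtained to confirm eligibility, before randomization.
- State it as an explicit exception to the rule that baseline variables are coded in categories.
- Treat its inclusion in the censoring-weight models as optional, since few dropouts are expected, and say which choice is made.

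If the sponsor prefers to keep the present list, one sentence giving the reason would answer the point.

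The cost is a line or two of SAP text and one extra coefficient per model, with no new data. The downside is that nothing may be gained if NIHSS adds nothing beyond GCS.

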4.3.2 **Tracking Procedure.** All study center investigators and study coordinators must have an established relationship with their emergency department personnel and must be routinely notified of hemorrhagic and ischemic strokes. Each center will design a system for patient tracking that best suits its needs according to time, personnel, and the patient population. The study coordinator will be responsible for tracking subjects and scheduling appointments. The study coordinator will inform subjects of the follow-up expectations when informed consent is obtained, and will maintain contact through telephone calls and letters. The Clinical Coordinating Center (CCC) database will drive a monthly report and centers will receive emails listing subjects due for assessment and overdue for assessments. The study coordinator will be required to document in the VISION EDC system whenever subjects are lost to follow-up or assessments are overdue. A subject is only considered “lost to follow-up” if contact is not achieved at the day 365 visit.

Attempts to find and establish contact with a subject must be made at every follow-up time-point, even if unsuccessful at an earlier time-point. A subject lost to follow-up will not be tolerated; in such case the site investigator will be placed on a remediation plan to improve subject tracking.

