2.0. Objectives of the Study

2.1. Efficacy

The primary aim of this multicenter, international, randomized, open-label, phase 3 trial is to determine the efficacy of intra-clot catheter placement and aspiration of hematoma contents, followed by gentle clot irrigation with low dose recombinant tissue plasminogen activator (rt-PA), referred to as Minimally Invasive Surgery plus rt-PA (MIS+rt-PA). The primary hypothesis of this trial is that the MIS+rt-PA approach to intracerebral hemorrhage (ICH) management will result in more patients having overall better functional outcome at 365 days, as defined by the proportion of subjects with dichotomized, adjudicated modified Rankin Scale (mRS) score 0-3 vs. 4-6, when compared to the mRS scores for patients managed with standard aggressive medical treatment. Although the mRS includes a category for death, and hence the primary analysis incorporates mortality outcomes, in-hospital and 30-day mortality will also be examined as safety outcomes for the trial. Furthermore, 365-day mortality will be evaluated separately as a secondary efficacy outcome. An intent-to-treat (ITT) paradigm for the analyses will be incorporated. The MISTIE III trial will enroll a total of 500 eligible patients, 250 randomized each treatment arm (MIS+rt-PA or medical management). The power to detect (88%) is for an estimated effect size of 13% across all clot locations with this sample size (500).

Additional analyses of efficacy outcomes will evaluate the therapeutic benefit of MIS+rt-PA relevant to medical management in improving subjects' function and quality of life at 365 days post symptom onset as measured by extended Glasgow Outcome Scale (eGOS), days in various locations such as home

Minimally Invasive Surgery Plus rt-PA for ICH Evacuation Phase 3

during the 365-day period, patient disposition at 180 and 365 days including proportion of days in longterm care facilities, National Institutes of Health Stroke Scale (NIHSS), Barthel score, days in hospital, days in intensive care unit (ICU), Stroke Impact Scale (SIS), Preference-Based Stroke Index (PBSI), EuroQol-5 Dimension (EQ-5D), Mini-Mental State Examination (MMSE), Personal Health Utility Interview, and Center for Epidemiological Studies – Depression (CES-D).

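### The primary TMLE in SAP 11.1, as written, makes almost no use of the observed 365-day mRS of patients who missed the 30- or 180-day visit

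*SAP*

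**What the plan says.** SAP 11.1 builds the primary estimate in three backward steps.

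- **Uncensored.** C at a visit marks a patient as uncensored; for example, C180=1 "means the participant attended the 180-day visit and had his or her mRS" recorded.
- **Weights.** W180 and W365 multiply probabilities that condition on C30=1 and C180=1. The censoring models are fitted only among those who attended the previous visit.
- **Model (1)** is fitted on all patients with C365=1. After that, "for each participant who is uncensored at 180 days (the previous visit), this model fit is used to generate the predicted probability"; this is S180.
- **Model (2)** regresses S180 among those with C180=1 and gives S30 for those with C30=1.
- **Model (3)** is fitted "using all participants who are uncensored at 30 days". Its predictions are averaged over every participant under each arm.
- **Missed interim visits.** The missing 30- or 180-day mRS is set to its most probable value before the other steps. "We do not apply this process to the final outcome at 365 days". Model (1) gains the term C30·C180 and its interaction with arm; model (2) gains C30 and its interaction with arm. These terms show whether the score was measured or predicted.

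Protocol 4.3.2 makes the pattern foreseeable: "Attempts to find and establish contact with a subject must be made at every follow-up time-point, even if unsuccessful at an earlier time-point".

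**The concern.** A patient who misses an interim visit but is assessed at day 365 has a known primary outcome. Nothing about that patient's endpoint is missing, so no missing-data model is needed for it. If the algorithm cannot carry that outcome into the final average, the trial loses precision. It also relies on a missing-at-random assumption, for patients whose endpoint is in hand, that the data could have made unnecessary. If missed visits go with outcome differently in the two arms, the risk difference shifts. SAP 11.1 includes the fill-in to keep these patients in the analysis, so the question is whether the later steps let it work.

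**Working it through.** **Plan's own figure.** For 250 per arm, 25% versus 38% and two-sided alpha 0.05 ("The primary analysis of efficacy is tested at the two-sided alpha level of 0.05"):

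- SE under the alternative = √[(0.25×0.75 + 0.38×0.62)/250] = 0.0411
- SE under the null = √[2×0.315×0.685/250] = 0.0415
- power = Φ[(0.13 − 1.96×0.0415)/0.0411] = Φ(1.18) = 88%

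This reproduces the planned figure. SAP 11.1 gives no figure for missed interim visits.

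**Following the outcome through the models.** With an intercept, arm, C30·C180 and the interaction, model (1) has a separate weighted level for each arm-by-flag cell. Outcomes of patients with C30·C180=0 set the level of their own cell. They reach fully observed patients only through the shared slopes for the baseline variables and M180.

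| Pattern, day-365 mRS known | Model (1) | Next step | Final step |
|---|---|---|---|
| Missed day 180 only | Own level | No S180, so not in model (2) | In model (3) with a value predicted from M30, not the observed outcome |
| Missed day 30 only | Own level | S180 made; in model (2) C30 and its interaction absorb it | No S30, not in model (3) |
| Missed both | Own level | No S180 | No S30, not in model (3) |

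C cannot have been reset to 1 after the fill-in. If it had been, C30·C180 would be constant and the added terms redundant. The fill-in also covers permanent dropouts, so it cannot define who is still at risk.

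**Weights.** For a patient with C180=0, the last factor of W365 conditions on an event that did not happen. A programmer could extrapolate the fitted model using the filled-in score, but the SAP does not say so.

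**Check of the mechanism by simulation.** Settings: the stated algorithm with N=500, about 25% versus 38% good outcome, deaths carried as mRS 6, modal fill-in and weights capped at 20. One day-365 outcome was changed at a time; units are 1/250.

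| Assumed missed per visit | Missed-visit patient: mean (mean absolute) | Fully observed patient: mean |
|---|---|---|
| 2% | 0.01 (0.06) | 1.05 |
| 5% | 0.00 (0.07) | 1.11 |
| 10% | −0.01 (0.10) | 1.23 |

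This measures leverage. It confirms the algebra and is not an error in the estimate.

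**Cost in precision, as written against corrected at-risk sets.** The variance ratio is about 1.04–1.06 at 3% missed per visit and 1.08–1.09 at 6%. Other simulated populations (120 to 300 replicates, so less precise) gave 1.07/1.02 = 1.05 at 3%, and between 1.13/1.02 = 1.11 and 1.16/1.03 = 1.13 at 6%. For scale, multiplying both SEs above by √1.04 = 1.020 gives Φ(3.160/1.020 − 1.979) = 87%. By √1.09 = 1.044 it gives Φ(3.160/1.044 − 1.979) = 85%.

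**Bias.**

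- Misses unrelated to outcome: no material bias. For example, at 5% per visit the mean risk difference was 0.135 with full data and 0.134 as written.
- Miss probability doubled for MIS-arm patients with bad outcomes (assumption): about 0.006 at 3% and 0.013 at 6%. A different simulated population gave 0.149 − 0.130 = 0.019 at 5%; corrected at-risk sets gave 0.132 there.
- Rough upper figure by hand: ignore deaths (who cannot miss a visit) and give no credit to measured interim scores. With miss rate m, the MIS-arm rate becomes 0.38(1−m)² / [0.38(1−m)² + 0.62(1−2m)²]. At m=0.03 this is 0.3575/0.9054 = 0.395 (+0.015). At 0.05 it is 0.3430/0.8452 = 0.406 (+0.026). At 0.06 it is 0.3358/0.8159 = 0.412 (+0.032). The simulated values lie below these, as they should.

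**The case against.** The strongest reply is that the effect is small and rests on invented rates. That largely stands. The only related figure in the documents is the 2% overall loss to follow-up in a previous trial (SAP 9.0), which is a different quantity. Tracking at every time-point (Protocol 4.3.2) and the locally recorded score kept as backup (Protocol 10.3.4) should keep interim misses few. The planned longitudinal analysis (SAP 11.2.2) does not require attendance at day 30 or 180, but it is exploratory and does not repair the primary estimate.

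Three stronger readings are tempting, and the documents do not support them.

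- **That intention-to-treat is breached.** SAP 5.2 defines it by assigned arm, and the last step of 11.1 predicts for every participant in both arms. All randomized patients stay in the estimand; some observed outcomes are used inefficiently.
- **That deaths would be censored.** A dead patient cannot attend a visit, so the worded example of C180=1 does not fit deaths. But 11.1 describes censoring as dropout, that sentence is an illustration, SAP 2.1 says the primary analysis incorporates mortality, and the outcome is 0–3 versus 4–6. What is missing is one line of definition.
- **That the leverage measures the error.** Switching all missed-visit MIS-arm outcomes from bad to good moves the arm mean by 0.000 as written and 0.084 when they are counted, at 5% missed per visit. Nothing in the documents suggests such a pattern.

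**Conclusion.** The point holds: section 11.1, followed as written, makes almost no use of known 365-day outcomes of patients with a missed interim visit, and it leaves their weights unstated. The algebra does not depend on the simulations; the size does.

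At an assumed 3% to 6% missed per visit:

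- extra variance of roughly 4% to 9% compared with the corrected version;
- no material bias if misses are unrelated to outcome;
- about 0.006 to 0.013 in the risk difference under the assumed doubling of misses among MIS-arm patients with bad outcomes. That is about 0.15 to 0.3 of the planning SE of 0.041. The 0.019 at 5% in another simulated population shows that this range depends on the settings.

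The effect is modest, but it is avoidable because the outcomes are observed. Neither the planned power nor the choice of estimator is in question.

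**What to change.** Amend SAP 11.1 before unblinding.

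1. Define a patient as at risk (uncensored) at visit v if the mRS is known at v or at any later visit. In the same sentence, state that a death counts as an observed mRS 6 at all later visits.
2. Use this definition in the censoring models behind W30, W180 and W365, in generating S180 and S30, and in the fitting sets of models (1) to (3). Permanent dropouts remain censored from their last known visit onward.
3. Keep the fill-in for missed interim scores. Keep C30·C180 and C30, with their arm interactions, as separate measured/imputed flags that no longer decide who is at risk.
4. Carry the same definition to the day-180 repeat of the method (SAP 13.5.a).
5. Tabulate, blinded, how many patients missed day 30 or day 180 but have a 365-day mRS, so that the assumed 3% to 6% is replaced by the trial's own count.

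The cost is a few sentences in the SAP and a few lines of code; no new data are needed. In simulation the corrected sets gave these patients about full weight (ratio 1.01) and removed nearly all of the bias.
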